3. ABBREVIATIONS

Abbreviations pertain to the SAP only (not the TFLs).

$\alpha v \beta 6$	alpha v beta 6
AE	adverse event
ALAT	Latin American Thoracic Association
ALOX5	arachidonate 5-lipoxygenase
ALT	alanine aminotransferase
AST	aspartate aminotransferase
ATS	American Thoracic Society
BAL	bronchoalveolar lavage
BUN	blood urea nitrogen
CBC	complete blood count
CSR	clinical study report
CV	coefficient of variation
DL_{co}/Hb	carbon monoxide diffusion capacity, corrected for hemoglobin
DSMB	Data Safety Monitoring Board
ECG	electrocardiogram
ERS	European Respiratory Society
ETS1	v-ets erythroblastosis virus E26 oncogene homolog 1
FEV ₁	a ratio of the forced expiratory volume in one second
FN1	fibronectin
FU	follow-up
FVC	forced vital capacity
GGT	gamma-glutamyl transpeptidase
HCO ₃	bicarbonate
HRCT	high resolution computed tomography
ICH	International Conference on Harmonization
I/E	inclusion/exclusion

IPF	idiopathic pulmonary fibrosis
JRS	Japanese Respiratory Society
LDH	lactate dehydrogenase
LDL	low density lipoprotein
MCH	mean corpuscular hemoglobin
MCHC	mean corpuscular hemoglobin concentration
MCV	mean corpuscular volume
MD	multiple dose
MedDRA	Medical Dictionary for Regulatory Activities
mRNA	messenger ribonucleic acid
NA	not applicable
OLR1	oxidized low density lipoprotein receptor 1
O ₂	oxygen
PAI-1	plasminogen activator inhibitor-1 (SERPINE1)
PFT	pulmonary function test
PK	pharmacokinetic
pSMAD2	phosphorylated SMAD2
PT	preferred term
RV	residual volume
SAP	Statistical Analysis Plan
SC	subcutaneous(ly)
SD	standard deviation
SE	standard error
SLB	surgical lung biopsy
SOC	system organ class
SOP	Standard Operating Procedure
TEAE	treatment emergent adverse event
TESAE	treatment emergent serious adverse event
TFLs	Tables, Figures, and Listings
TGF- β	transforming growth factor-beta
TGM2	transglutaminase 2

TREM1 triggering receptor expressed on myeloid cells 1
tSMAD2 total SMAD2
UIP usual interstitial pneumonia

4. INTRODUCTION

The intent of this document is to provide guidance for analyses of data for this Phase 2a study. This statistical analysis plan (SAP) has been developed after review of the Clinical Study Protocol 203PF201 (version 4 dated 16 July 2015).

This SAP describes the planned analyses to evaluate the safety, tolerability, pharmacokinetics (PK), immunogenicity, and impact on bronchoalveolar lavage (BAL) and peripheral blood biomarkers of multiple doses of STX-100 (BG00011) in subjects with idiopathic pulmonary fibrosis (IPF). Please note that study drug names STX-100 and BG00011 are equivalent, and the study drug will be referred to as BG00011 in the SAP and associated tables, figures, and listings (TFLs). A detailed description of the planned TFLs to be presented in the clinical study report (CSR) is provided in the accompanying TFL shell document. This SAP must be finalised prior to the lock of the clinical database and unblinding for this study. When the SAP and TFL shells are agreed upon and finalized, they will serve as the template for this study's CSR.

This version 2.0 SAP supersedes the statistical considerations identified in the protocol and the statistical considerations identified in the version 1.0 SAP dated 06 March 2012; where considerations are substantially different, they will be so identified. If additional analyses are required to supplement the planned analyses described in this SAP, they will be identified in the CSR. Any substantial deviations from this SAP will be agreed upon between Biogen MA Inc. and [REDACTED] and identified in the CSR.

This SAP is written with consideration of the recommendations outlined in the International Conference on Harmonization (ICH) E9 Guideline entitled Guidance for Industry: Statistical Principles for Clinical Trials¹ and the ICH E3 Guideline entitled Guidance for Industry: Structure and Content of Clinical Study Reports².

5. STUDY OBJECTIVES

Primary Objective:

- To evaluate the safety and tolerability of subcutaneously (SC) administered, multiple escalating doses of BG00011 (humanized monoclonal antibody directed against the $\alpha v \beta 6$ integrin) in subjects with IPF

Secondary Objectives:

- To estimate the PK parameters after the first dose and after the last dose of multiple, escalating doses of BG00011 in subjects with IPF
- To assess the immunogenicity of BG00011 in subjects with IPF

- To assess the effect of BG00011 on biomarkers isolated from BAL and peripheral blood in subjects with IPF

6. STUDY DESIGN

This is a multi-center, randomized, double-blind, placebo-controlled, multiple dose, dose-escalation study designed to evaluate the safety, tolerability, PK, immunogenicity, and impact on BAL and peripheral blood biomarkers of BG00011 activity in subjects with IPF conducted at approximately 15 centers in North America.

Approximately 40 subjects will be enrolled into 5 sequential ascending dose cohorts ([Table 1](#)). Cohorts will include 8 subjects randomized to receive either BG00011 (6 subjects) or placebo (2 subjects). Additional subjects may be enrolled if deemed appropriate by the Data Safety Monitoring Board (DSMB). Doses to be administered are as follows:

Table 1: Dosing Cohorts

Cohort	Dose	Number of Subjects	
		BG00011	Placebo
1	0.015 mg/kg	6	2
2	0.1 mg/kg	6	2
3	0.3 mg/kg	6	2
4	1.0 mg/kg	6	2
5	3.0 mg/kg	6	2
Total Number of Subjects		30	10

Subjects with clinical symptoms and features consistent with IPF prior to screening; forced vital capacity (FVC) \geq 50% of predicted value; carbon monoxide diffusion capacity, corrected for hemoglobin (DL_{CO}/Hb) \geq 30% of predicted value; oxygen (O₂) saturation $>$ 90% while breathing ambient air at rest or receiving \leq 2 L/minute of supplemental oxygen; residual volume (RV) \leq 120% of predicted value; a ratio of the forced expiratory volume in one second (FEV₁) to FVC \geq 0.65 after the use of a bronchodilator during screening pulmonary function tests (PFTs); high resolution computed tomography (HRCT) consistent with usual interstitial pneumonia (UIP) pattern; and who meet the other inclusion/exclusion (I/E) criteria are eligible to enroll in the study. Subjects who do not qualify for study eligibility may be rescreened at the discretion of the Principal Investigator.

Each subject within a dose cohort will be randomized to receive either BG00011 or placebo and will participate in 2 consecutive study periods: 1) each subject will receive 8 consecutive weekly doses of BG00011 (or placebo) (Period 1; Multiple Dose [MD] phase); and, 2) each subject will be monitored for 12 weeks (8 weeks for Cohorts 4 and 5) following administration of the last dose of study drug (Period 2; Follow-Up [FU] Phase).

6.1 NOMENCLATURE FOR STUDY PERIODS AND STUDY DAYS

Days for the MD period are designated with an “MD” and days for the FU period are designated with an “FU.”

- Day 1-MD is the day the subject receives the first dose during the MD period of the study.
- Day 1-FU is first day of the follow-up period, which should coincide with the day of last dose during the MD period (Day 50-MD).

7. TREATMENT

BG00011 will be administered as an SC injection. Doses will be 0.015 mg/kg, 0.1 mg/kg, 0.3 mg/kg, 1.0 mg/kg, and 3.0 mg/kg. Weight obtained at initial screening will be used to calculate dose throughout the study. At the end of a screening period, eligible subjects will return for dosing on Day 1-MD. Study drug will be administered once weekly for 8 doses (7 weeks), i.e., on Days 1-MD, 8-MD, 15-MD, 22-MD, 29-MD, 36-MD, 43-MD, and 50-MD of the multiple-dose period.

In cohorts 1 to 3, each subject’s participation in the study will be for approximately 24 weeks (~5.5 months), i.e., up to 5 weeks to perform screening/entry evaluations, followed by 7 weeks of double-blind study dosing (8 doses) and a Follow-up period of 12 weeks. For Cohorts 4 and 5, the subject’s participation in the study will be for approximately 23 weeks (~5.5 months), i.e., up to 8 weeks to perform screening/entry evaluations, followed by 7 weeks of double-blind study dosing (8 doses) and Follow-up period of 8 weeks.

8. SAMPLE SIZE JUSTIFICATION

No formal statistical justification for the sample size was performed for this Phase 2a study. Cohort size was determined based on requirements for PK analyses and safety assessments. With 6 subjects per cohort administered BG00011 the probability of observing an event is 82% if the actual probability of such an event is 25%.

9. DEFINITION OF ANALYSIS POPULATIONS

The “Safety” population will consist of all subjects who received at least one dose of BG00011 or placebo.

The “Pharmacodynamic” population will consist of all subjects who received at least 1 multiple dose injection of BG00011 and have a corresponding sample collected for BAL and/or blood biomarkers (e.g., Visit 16 Day 8-FU).

All protocol deviations that occur during the study will be considered for their severity/impact prior to treatment assignment unblinding and will be taken into consideration when subjects are assigned to analysis populations. Details of subject assignment to the analysis populations will be listed.

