10. STATISTICAL METHODOLOGY

10.1 General

Data listings will be provided by treatment group, subject and visit, if applicable. Summary statistics and statistical analyses will only be presented for data where detailed in this SAP. For continuous data, summary statistics will include the arithmetic mean, arithmetic standard deviation (SD), median, minimum (Min), maximum (Max) and n; for log-normal data the geometric mean and geometric coefficient of variation (CV) will also be presented. For categorical data, frequency count and percentages will be presented. Data listings will be provided for all subjects up to the point of withdrawal, with any subjects excluded from the relevant population highlighted. Summary statistics and statistical analyses will generally only be performed for subjects included in the relevant analysis population. For the calculation of summary statistics and statistical analysis, unrounded data will be used.

Due to the small number of subjects expected to enroll at each participating center, all summaries and analyses will be performed using data pooled across centers. Data for BG00011 treated subjects will be grouped by treatment group. Data for all placebo subjects, regardless of treatment group, will be treated as one group. Data will be summarized and presented by treatment group, defined as each of the BG00011 dose groups and the combined placebo group. Data will be listed by treatment group. Exposure to study medication will be tabulated by treatment group.

Mean change from baseline is the mean of all individual subject’s change from their baseline value. Each individual change from baseline will be calculated by subtracting the individual subject’s baseline value from the value at their subsequent visit(s). The individual subject’s change from baseline values will be used to calculate the mean change from baseline using a SAS[®] procedure such as Proc Univariate.

Data analyses will be performed using SAS[®] Version 9.1.3 or greater.

As previously stated (Section 4), this document describes the planned analyses for this Phase 2a study evaluating the safety, tolerability, PK, immunogenicity, and impact on BAL and peripheral blood biomarker of multiple doses of BG00011 in subjects with IPF. Some of the analyses described in this SAP will be performed by outside vendors. These data will be imported to the Biometrics database for study 203PF201 or, alternatively, provided as separate reports.

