10.2 Definitions

The following definitions apply:

Baseline - last observation collected prior to the date/time of study drug administration, unless otherwise noted.

Treatment group - each of the five BG00011 dose groups and the combined placebo group.

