10.3 Demographics and Baseline Characteristics

Subject disposition will be summarized for the safety and efficacy populations. Reasons for discontinuation will be summarized by treatment group. The demographic variables age, sex, race, ethnicity, body weight, height, and body mass index will be summarized. By-subject listings of these variables will be provided.

Listings will also be created for subject eligibility, smoking history, and general/IPF-specific medical history.

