10.8 Safety and Tolerability Assessments

Data will be summarized and presented by treatment group, defined as each of the BG00011 dose groups, the combined BG00011 group, and the combined placebo group. Data will be listed by treatment group. The safety population will be used for the following safety analyses. No inferential statistical analyses are planned.

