10.8.7 Bronchoalveolar Lavage (BAL) MMP-12

A BAL will be performed during the screening period and after receiving the last dose of study medication (i.e., from Visit 14 Day 3-FU to Visit 16 Day 8-FU). Analysis of the BAL macrophage MMP-12 mRNA levels (which are increased when macrophages are activated) will be measured.

Subject listings of the screening and Visit 16 Day 8-FU MMP-12 levels, as well as the % change from screening, will be provided. Summary statistics of the relative expression of MMP-12 levels at screening and following the last dose of study medication, as well as the percent change from Screening, will also be provided for each treatment group.

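### The Pharmacodynamic population admits only BG00011 recipients, so the biomarker summary tables that must show placebo would have none

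*SAP*

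**What the plan says.** Section 9 defines two populations. Safety takes anyone dosed with either BG00011 or placebo. Pharmacodynamic takes "all subjects who received at least 1 multiple dose injection of BG00011 and have a corresponding sample collected" for BAL and/or blood biomarkers, with no mention of placebo.

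Four other places bear on who should appear in the biomarker tables:

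- Section 5 gives a secondary objective: "To assess the effect of BG00011 on biomarkers isolated from BAL and peripheral blood in subjects with IPF".
- Section 10.1 states: "Summary statistics and statistical analyses will generally only be performed for subjects included in the relevant analysis population".
- Section 10.1 also states: "Data will be summarized and presented by treatment group, defined as each of the BG00011 dose groups and the combined placebo group". Section 10.2 repeats this as a definition: "Treatment group - each of the five BG00011 dose groups and the combined placebo group".
- Section 10.10 (Pharmacodynamic Analyses) promises listings and summary tables for seven genes and for the pSMAD2/tSMAD2 ratio, split by treatment group and visit. It names no analysis population.

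Section 13 records that version 2.0 renamed the former Efficacy population and lowered the requirement from five injections to one. It too describes the injection as BG00011.

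**The concern.** The population rule and the table specification cannot both be followed. One excludes every placebo subject; the other calls for a placebo column.

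The trial is randomised and placebo-controlled, and Section 10.10 plans only descriptive output. The placebo column is therefore the only untreated reference in these summaries. Without it, a reader can compare visits within a dose group, or one dose with another, but cannot set the course on BG00011 beside the course on placebo over the same visits. A shift due to time, disease course or repeat sampling could then be mistaken for a drug effect.

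**Working it through.** **Which population governs Section 10.10.** Section 9 offers only two. Safety is assigned to the Section 10.8 analyses: "The safety population will be used for the following safety analyses". The other is called Pharmacodynamic and is built on possession of a BAL or blood biomarker sample. It is the natural population for a section titled Pharmacodynamic Analyses, and nothing points the analyst to Safety instead.

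**Whether BG00011 could simply mean study drug.** Section 4 equates BG00011 with STX-100 only. Where the SAP means both arms it says so: the Safety definition just above, Section 6 and Section 10.9 all name placebo alongside BG00011. Sections 7 and 10.6 use neutral terms for the study treatment. The Pharmacodynamic definition uses neither form.

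**Head count (Table 1, planned enrolment).**

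- BG00011: 5 cohorts × 6 = 30, matching the table total.
- Placebo: 5 cohorts × 2 = 10, matching the table total.
- All subjects: 30 + 10 = 40.

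| | Definition as written | With placebo added |
|---|---|---|
| BG00011 eligible (maximum) | 30 | 30 |
| Placebo eligible (maximum) | 0 | 10 |
| Total (maximum) | 30 | 40 |
| Filled columns | 5 | 5 + 1 = 6 |

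The share of planned subjects excluded is 10/40 = 25%. The lost column is the largest one: up to 10 subjects, against 6 per dose group.

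**Measures affected.** Section 10.10 covers 7 genes + 1 ratio = 8. Section 10.8.7 adds a ninth biomarker, MMP-12, for which the SAP plans "Summary statistics of the relative expression of MMP-12 levels at screening and following the last dose of study medication". That section falls under 10.8 and so uses the Safety population, and MMP-12 keeps its placebo column. The conflict therefore touches 8 of 9 measures (89%), or all 8 of those in Section 10.10.

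**Listings.** Section 10.1 keeps all subjects in listings and highlights those outside the population. Placebo biomarker values would still be listed; only the summary tables lose them.

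**The case against.** The strongest reply is that the conflict is inferred. Section 10.10 names no population, the restriction in Section 10.1 is softened by the word *generally*, and Sections 10.1, 10.2 and 10.10 together plainly call for a placebo column. A programmer following them might well produce one. On this view the Section 9 wording is a slip for study drug. Section 9 itself lends some support: protocol deviations are weighed before unblinding and feed into population assignment, and a criterion based on receipt of BG00011 could not be applied while arms are masked. The TFL shells, which are not at hand, may also settle the matter.

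A slip is indeed likely, and the shells cannot be checked. Neither point removes the conflict. Section 13 carries the same BG00011 wording into its account of the version 2.0 rule, so the current text is consistent in leaving placebo out. The leeway in Section 10.1 does not say which rule gives way. The masking point is a further reason to correct the definition, since a rule naming both arms can be applied blind.

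Two limits on the consequence stand. Within-group comparison over visits and comparison across doses would survive. The 8-of-9 figure depends on counting MMP-12, which sits among the safety assessments, in the denominator.

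**Conclusion.** The concern holds. Followed as written, Section 9 leaves 0 of 10 planned placebo subjects in the Section 10.10 summary tables, against up to 10 if placebo is named, and removes the summarised concurrent control for 8 biomarker measures. This rests on three assumptions: planned enrolment is met, the Pharmacodynamic population is the relevant one for Section 10.10, and its definition is applied literally.

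The effect is confined to descriptive tables for one secondary objective. No inferential test, primary safety result, MMP-12 summary or listing is affected. It should be fixed, because membership of an analysis population should not depend on a programmer guessing what was meant.

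**What to change.** Before unblinding:

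1. In Section 9, insert *or placebo* after BG00011 in the Pharmacodynamic definition, leaving the sample requirement as it is.
2. In Section 10.10, add one sentence naming the Pharmacodynamic population as the basis of its summary tables.
3. In Section 10.3, which reads "Subject disposition will be summarized for the safety and efficacy populations", replace the superseded name with Pharmacodynamic.
4. In Section 13, align the description of the one-injection rule with the corrected definition.

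The cost is one phrase, one sentence and two wording alignments. The tables are already planned by treatment group, so no analysis is added. If the SAP can no longer be revised before unblinding, Section 4 already provides for substantial deviations to be agreed and identified in the CSR, and the inclusion of placebo can be recorded there.

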10. STATISTICAL METHODOLOGY

10.1 General

Data listings will be provided by treatment group, subject and visit, if applicable. Summary statistics and statistical analyses will only be presented for data where detailed in this SAP. For continuous data, summary statistics will include the arithmetic mean, arithmetic standard deviation (SD), median, minimum (Min), maximum (Max) and n; for log-normal data the geometric mean and geometric coefficient of variation (CV) will also be presented. For categorical data, frequency count and percentages will be presented. Data listings will be provided for all subjects up to the point of withdrawal, with any subjects excluded from the relevant population highlighted. Summary statistics and statistical analyses will generally only be performed for subjects included in the relevant analysis population. For the calculation of summary statistics and statistical analysis, unrounded data will be used.

Due to the small number of subjects expected to enroll at each participating center, all summaries and analyses will be performed using data pooled across centers. Data for BG00011 treated subjects will be grouped by treatment group. Data for all placebo subjects, regardless of treatment group, will be treated as one group. Data will be summarized and presented by treatment group, defined as each of the BG00011 dose groups and the combined placebo group. Data will be listed by treatment group. Exposure to study medication will be tabulated by treatment group.

Mean change from baseline is the mean of all individual subject’s change from their baseline value. Each individual change from baseline will be calculated by subtracting the individual subject’s baseline value from the value at their subsequent visit(s). The individual subject’s change from baseline values will be used to calculate the mean change from baseline using a SAS[®] procedure such as Proc Univariate.

Data analyses will be performed using SAS[®] Version 9.1.3 or greater.

As previously stated (Section 4), this document describes the planned analyses for this Phase 2a study evaluating the safety, tolerability, PK, immunogenicity, and impact on BAL and peripheral blood biomarker of multiple doses of BG00011 in subjects with IPF. Some of the analyses described in this SAP will be performed by outside vendors. These data will be imported to the Biometrics database for study 203PF201 or, alternatively, provided as separate reports.

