10.9 Data Safety Monitoring Board

An independent DSMB experienced in the oversight and monitoring of the conduct of clinical trials will determine whether dose escalation should proceed. The DSMB will be comprised of a biostatistician and two pulmonologists with expertise in interstitial lung diseases. The DSMB members' responsibilities and the process for data reviews and dose-escalation are described in the DSMB Charter.

Dose escalation will be based on the DSMB's review of unblinded PK and safety data through Day 15 from the initial 4 (of 8) subjects administered BG00011 or placebo (3:1, respectively) in each cohort. Safety assessments will include a review of AEs, vital signs, physical examination, clinical laboratory tests, and pulse oximetry from these visits. In order to allow for compilation and evaluation of the data, it is anticipated that the DSMB will convene approximately 9-10 weeks after the first 4 subjects in the previous cohort are initially dosed.

Serious adverse events will be provided to the DSMB on an ongoing basis throughout the study. Updated safety (including BAL, PFTs, and HRCT results) and PK information on all participants will be provided in each subsequent DSMB data package. For example, at the DSMB meetings for Cohorts 2 and 3, updated safety and PK data will be available through at least week 8 of the follow-up period (i.e., complete PK data through the dosing phase and follow-up BAL, PFT, and HRCT) for all participants in Cohorts 1 and 2, respectively.

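### Each dose is shown only against placebo pooled over five cohorts, yet follow-up is 12 weeks in Cohorts 1-3 and 8 weeks in Cohorts 4-5, so crude TEAE incidence favours the two top doses

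*SAP*

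**What the plan says.** Section 6 sets a sequential design: "Approximately 40 subjects will be enrolled into 5 sequential ascending dose cohorts", each randomised as 6 BG00011 and 2 placebo. Section 10.1 then pools the controls: "Data for all placebo subjects, regardless of treatment group, will be treated as one group". Section 10.2 defines the treatment groups to match, as "each of the five BG00011 dose groups and the combined placebo group". For safety, Section 10.8 adds a combined BG00011 group and says that no inferential analysis is planned.

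Conduct differs by cohort. In Cohorts 1-3, Section 7 gives up to 5 weeks of screening, 7 weeks of dosing and 12 weeks of follow-up. In Cohorts 4 and 5 it gives "up to 8 weeks to perform screening/entry evaluations, followed by 7 weeks of double-blind study dosing (8 doses) and Follow-up period of 8 weeks".

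Section 10.8.1 counts an event as treatment-emergent from the first dose onwards and states no end to that window. Incidence is the number of subjects with the event divided by the number in the treatment group. The SAP text asks for no placebo display by cohort, no common window and no adjustment for time observed.

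**The concern.** Randomisation is within cohort. For any one dose, 2 of the 10 pooled placebo subjects were randomised alongside it and 8 in other cohorts, so a single dose column beside the pooled placebo column is not a purely randomised comparison. Whatever differs between cohorts also differs between doses.

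One such difference is written into the plan. The two highest-dose cohorts are watched for four weeks less than the other three, and pooled placebo mixes both lengths. A crude proportion rises with time at risk, so subjects on 1.0 and 3.0 mg/kg would show fewer TEAEs than pooled placebo even if the drug did nothing. Safety and tolerability are the primary objective, and the distortion is in the reassuring direction at the top doses.

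**Working it through.** **The plan's own figures.** Section 6: 5 × 6 = 30 BG00011 and 5 × 2 = 10 placebo, as in Table 1. Section 7, total participation: 5 + 7 + 12 = 24 weeks (Cohorts 1-3) and 8 + 7 + 8 = 23 weeks (Cohorts 4-5), as stated. The totals nearly agree only because longer screening offsets shorter follow-up.

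**Planned time from first dose** (Sections 6 and 7, assuming everyone completes):
- Cohorts 1-3: 7 + 12 = 19 weeks
- Cohorts 4-5: 7 + 8 = 15 weeks
- Pooled placebo, 6 subjects from Cohorts 1-3 and 4 from Cohorts 4-5: (6 × 19 + 4 × 15) / 10 = 17.4 weeks
- Ratio of pooled placebo to Cohorts 4-5: 17.4 / 15 = 1.16

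**Effect on crude incidence with no drug effect.** Let F(t) be the probability of a first event by week t. Pooled placebo has expected incidence 0.6 F(19) + 0.4 F(15). Cohorts 4-5 minus pooled placebo is then −0.6 × [F(19) − F(15)], and Cohorts 1-3 minus pooled placebo is +0.4 × [F(19) − F(15)]. Only first events between weeks 15 and 19 matter.

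The SAP gives no event rate. Assume F(t) = 1 − exp(−rt) with r from 0.01 to 0.05 per week:

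| r per week | Cohorts 1-3, F(19) | Cohorts 4-5, F(15) | Pooled placebo | Cohorts 4-5 minus placebo |
|---|---|---|---|---|
| 0.01 | 17.3% | 13.9% | 16.0% | −2.0 points |
| 0.02 | 31.6% | 25.9% | 29.3% | −3.4 points |
| 0.05 | 61.3% | 52.8% | 57.9% | −5.1 points |

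Under a constant rate the gap is largest at r = ln(19/15)/4 = 0.059, where it is 0.6 × (exp(−15 × 0.059) − exp(−19 × 0.059)) = 5.2 points. It is below 2 points for rates under about 0.01.

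**Balance of the combined contrast.** Of the 30 BG00011 subjects, 18 are in Cohorts 1-3 (60%), as are 6 of the 10 placebo subjects (60%). Both combined groups average 17.4 weeks, so that contrast is not distorted, but it says nothing by dose.

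**Precision of the alternatives**, as SE = SD × sqrt(1/n1 + 1/n2):
- one dose against pooled placebo, 6 vs 10: 0.516 SD
- one top dose against Cohort 4-5 placebo, 6 vs 4: 0.645 SD
- Cohorts 4-5 together, 12 vs 4: 0.577 SD (merges two doses)
- Cohorts 1-3 together, 18 vs 6: 0.471 SD (merges three doses)

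**When pooling is still the better estimate.** Suppose a drug-free outcome shifts by d SD between Cohorts 1-3 and 4-5. A top dose against pooled placebo is biased by d − 0.4d = 0.6d. Pooling has the lower mean squared error than 6 vs 4 while 0.36d² + 0.267 < 0.417, that is, for d below about 0.65 SD.

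**The case against.** The strongest reply is that pooling is declared openly, is usual for this design, and feeds descriptive tables only. Two concurrent controls per dose cannot stand alone, and the last calculation shows pooling to be the better estimate over a wide range of possible shifts. All of that stands, and it is why the pooled column should stay. It does not answer the follow-up difference, because a descriptive table is still read across its columns.

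Section 10.8 already plans combined BG00011 against combined placebo, which is balanced. That also stands, but it does not help a reader judging the two top doses.

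A reader might infer more: that PFT, BAL, HRCT and biomarker readings at the top doses are also distorted, or that drift in case mix, care or assays is established. The SAP does not support this.
- PFTs are compared at Day 29-MD and Day 8-FU, BAL is taken from Day 3-FU to Day 8-FU, and HRCT is within 21 days of the last dose. All come before the shorter follow-up ends.
- The longer screening allowance could lengthen the interval from screening for MMP-12 and HRCT, but it is a maximum and actual intervals are unknown.
- The PFT baseline rule changed with protocol version, but the SAP does not map versions to cohorts.
- Four escalation steps of 9-10 weeks (Section 10.9) put Cohort 5 some 36-40 weeks or more after Cohort 1. Elapsed time alone is not evidence of drift.
- Nor are the top doses necessarily worst placed for general drift: if it were linear over cohorts, Cohort 1 would be biased as much as Cohort 5, in the opposite direction.

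Listing layouts are in a separate TFL shell document, so cohort labels may already be planned there.

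**Conclusion.** The point holds for crude TEAE incidence. Planned observation is 15 weeks in Cohorts 4-5 against an average of 17.4 weeks in pooled placebo, which follows from the SAP alone. The resulting advantage to the two top doses, about 2 to 5 percentage points with no drug effect, rests on three assumptions: a constant first-event rate of 0.01 to 0.05 per week, full completion, and event collection to the end of follow-up. If first events cluster in the dosing period, the gap is smaller.

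The size is modest: one subject in a dose group of 6 is 16.7 points. But the direction is known, it touches the primary objective, and it can be removed without new data. Other changes between cohorts would line up with dose too. Their size is not in the documents, so they justify a sensitivity display and not a claim of bias. Pooling itself is not the error.

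**What to change.** Before database lock and unblinding:

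1. Keep the pooled placebo column as the main display.
2. In Section 10.8.1, summarise TEAEs over a window common to all cohorts, through 8 weeks after the last dose, or per unit of observation time. The common window is simpler and needs no constant-rate assumption. Later events in Cohorts 1-3 remain in the listings.
3. For the TEAE overview and the key change-from-baseline safety summaries, add a descriptive sensitivity display of BG00011 against placebo within Cohorts 1-3 (18 vs 6) and within Cohorts 4-5 (12 vs 4). Note beside it that each pair merges doses and is imprecise.
4. State that each placebo subject's cohort is identified in listings.

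The within-block display should not become a confirmation rule. Requiring a difference in Cohorts 4-5 to reappear against four placebo subjects could discount a real safety signal through noise.

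If the same pairs are wanted for the Section 10.10 biomarkers, Section 9 must be reworded first: as written, the Pharmacodynamic population requires an injection of BG00011 and so leaves out placebo subjects.

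The cost is SAP and shell wording and a few extra columns with placebo groups of 4 and 6, which will be noisy. No new data are needed.
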